*** NOTE:**

Laboratory safety and efficacy endpoints will be studied at the visits by the central lab. For hospitalized patients, local labs will perform, in addition, analyses as required by the standard of care and this information will be entered in the study eCRF.

PRIMARY ENDPOINTS: EFFICACY

- The primary outcome is the time to first occurrence of disease reactivation (including full and partial disease reactivation) during the 16-week RW phase.

SECONDARY ENDPOINTS

Key Secondary Efficacy Endpoint

- Response to therapy (including complete response and partial response) in the SAOL phase from Week 10 onwards and observed at least at 2 consecutive visits at least 2 weeks apart during the SAOL phase

Other Secondary Efficacy Endpoints

- Best response to therapy during the SAOL phase (including complete response and partial response and disease improvement)
- Duration of response to therapy (including complete response and partial response) during the SAOL phase
- Disease reactivation rate for individual subjects (number of disease reactivations experienced per week while each subject is on the study treatment during the SAOL phase).
- Treatment failures (i.e. patients who experience at least one disease reactivation)
- Intensity of disease reactivations (defined by the level of activity given by the mAIDAI – both objective and subjective criteria)
- Serum CRP
- Serum Ferritin
- Improvement of fevers (if present at Baseline)
- Improvement of hepato/splenomegaly (if present at Baseline)
- Improvement in serum albumin and liver transaminases, anemia and/or platelet count (if present at Baseline)

- Hospital length of stay
- Physician Global Assessment
- Patient's/Caregiver's qualitative evaluation of health status
- Presence of skin rash (evolution if present at Baseline or appearance during the study)
- Tolerance to oral/enteral nutrition for hospitalized patients if intestinal dysfunction was present at Baseline
- Improvement of stool output for hospitalized patients if intestinal dysfunction was present at Baseline

During the SAOL phase, patient evolution will be described by plotting over time the mAIDAI, PGA, Ferritin, and CRP as well as the most prominent clinical features according to the individual patient profiles. Absolute and percentage of change from baseline will be calculated for continuous variables. Response to treatment in the initial active disease, number, frequency and severity of disease reactivations during the study will be compared to incidence and severity described in the medical history of individual patients.

- Secondary Safety and Tolerability Endpoints

- Adverse events [including AESI] will be reported
- Physical examination findings: clinically significant changes from Baseline
- Vital signs: clinically significant changes from Baseline
- Laboratory assessments (*): including clinically significant changes from Baseline in hematology with platelet counts, CRP, ESR, ferritin, fibrinogen, D-dimer, liver enzymes, (Note: all clinically significant abnormal laboratory results or assessments must be followed until they resolve (i.e., return to normal or Baseline values) or stabilize, or until they are judged by the Investigator to be no longer clinically significant)
- Immunogenicity evaluation: Generation of anti-recombinant human IL-18BP (anti-rhIL-18BP) antibodies
- Local tolerability at the injection site (evaluated by a standardized assessment)

(*) NOTE:

Laboratory safety and efficacy endpoints will be studied at the visits by the central lab. For hospitalized patients, local labs will perform, in addition, analyses as required by the standard of care and this information will be entered in the study eCRF.

CHARACTERIZATION OF THE PHARMACOKINETIC (PK) PROFILE OF TADEKINIG ALFA AFTER REPEATED S.C. INJECTIONS

Enrolled patients will be assessed for PK at V1 (week1) and V5 (week4). Additional sample for PK study will be collected at V1 and V5 prior to treatment and at 2 h, 4 h, 6 h and 24h post treatment (with a +/- 30 minute window at each sample collection). Trough levels are calculated based on blood samples used for lab testing taken at every visit prior to treatment administration (no extra sample needed). Patients who are not hospitalized will require separate study

visits at Week 0 / Day 2, and Week 4 / Day 29, and will need to present to the site 24 hours post-treatment for final PK sample collections, as well as AE and concomitant medication assessments.

PK Endpoints - Time to maximal concentration (T_{max}), the maximal concentration (C_{max}), trough concentration, area under the curve during the first 24 hours of treatment (AUC_{0-24}) and the elimination half-life will be determined in serum. The steady state concentration will be explored at V5 (week 4).

STOPPING RULE (S) FOR DISCONTINUING TREATMENT IN INDIVIDUAL PARTICIPANT

Patient withdrawal/Physician discontinuation

The physicians and the patients (or legal representative) will have the option to discontinue the treatment if they feel that pursuing the treatment is not appropriate.

The physician can decide anytime to start rescue immunosuppression and therefore discontinue the patient from the study*.

* All key safety and efficacy outcomes will be followed up. Patients will continue to come to the scheduled visits for safety and efficacy assessments.

Treatment discontinuation

The occurrence of adverse events of grades 3 and 4 of severity (section 16) may result in transient or permanent treatment discontinuation. If treatment interruption is more than 3 weeks, the subject will be permanently discontinued from the study.

Study discontinuation

Stopping of the study will be strictly determined for safety concerns.

At any time, the DSMB may recommend to the Sponsor the early termination of the study after reviewing study safety data including AEs, SAEs, and suspected unexpected serious adverse reactions (SUSARs).

At any time, the Sponsor may recommend terminating the study.

Conduct of telemedicine study visits

In order to protect the patient's and caregiver's safety and welfare during the COVID-19 pandemic, conduction of on-site study visits may not be considered appropriate; most patients have to travel to their study site and on-site study visits may expose both the patients and caregivers as well as study site personnel to an increased risk of infection.

Moreover, due to the ultra-rare indication of this study, conducting on-site study visits at sites often located far away from the patient's home has made study conduct challenging.

Thus, in an effort to accommodate the patients and their families while ensuring the relevant study data is collected, scheduled study visits (except for the Baseline visit) may be conducted as telemedicine visits involving the use of electronic communications (for example, live interactive video and

audio) to enable site staff to conduct “virtual” (not in-person) visits with their patients. These visits may be supported by home health nurses assisting in physical examination or performance of blood draws. Laboratory assessments may be also performed at qualified local laboratories. The study site may also utilize a physical examination from the patient’s most recent standard of care visit conducted by the local treating physician, for the purpose of the study.

Patients and/or parents (or legal representative, if applicable) will sign a respective assent/informed consent prior to the conduct of such telemedicine visits.

Further details about the different possibilities for the conduct of telemedicine visits are described in section 14.1.

STATISTICAL ANALYSIS

Statistical analysis:

Data will be analyzed on an intent-to-treat basis. Baseline patient and disease characteristics according to treatment arm will be presented using standard descriptive statistics.

Comparative statistical analyses will be performed on data collected during the RW phase. The primary endpoint is time to first occurrence of disease reactivation (including full and partial disease reactivation) during the RW phase. Tadekinig alfa will be compared to placebo using the log rank test at the alpha = 0.05 level of significance (2-sided). Kaplan-Meier estimates of the distribution of time-to-event will be summarized and graphed by treatment group.

To test the efficacy of Tadekinig alfa on secondary outcomes during the RW, Fisher's exact test will be utilized for binary outcomes (i.e. treatment failure rate) and a non-parametric, Mann-Whitney-Wilcoxon test will be utilized for continuous outcomes (i.e. change in the mAIDAI). To assess the impact of possible variation in baseline measures, an analysis of covariance (ANCOVA) model with covariate adjustment for Baseline may be considered as a sensitivity analysis, or alternative non-parametric approaches if normality assumptions are not met.

If the primary analysis is statistically significant ($p < 0.05$), the following secondary endpoints measured during the RW phase will be analyzed using a fixed-sequence testing procedure in the order specified below to control the overall level of significance:

- Treatment failure rate;
- Change from RW baseline to Week 34 (i.e. Week 16 of the RW phase) or End of Study Visit in the mAIDAI total score; and
- Change from RW baseline to Week 34 or End of Study Visit in the PGA symptom severity score.

For each of these endpoints, the treatment groups will be compared using a two-sided test at alpha = 0.05 level of significance. However, once a non-significant result (i.e. $p > 0.05$) occurs, the results of all subsequent analyses will be exploratory rather than confirmatory.

In addition, all endpoints will be evaluated descriptively including 95% confidence intervals for the mean and proportions.

Analysis of data collected during the SAOL phase will be descriptive in nature, to include 95% CIs around select mean estimates and proportions of interest. Absolute and percentage of change from baseline will be calculated for continuous variables. Response to treatment in the initial active disease, number, frequency and severity of disease reactivations during the study will be compared to incidence and severity described in the medical history of individual patients.

Individual subject's raw data will be captured with data listings and individual patient plots at each time point to visualize the different responses (e.g. in terms of mAIDAI, PGA, Ferritin and CRP as well as the most prominent

[figure not shown]
clinical features and results from patient's/caregiver's qualitative evaluation of health status) at each time point to the assigned treatment in a descriptive manner.

Power Calculations

The primary endpoint of the study is time to first occurrence of disease reactivation (including full and partial disease reactivation) during the RW phase of the study. There is limited historical data for this disease condition, for either a control or an experimental test product. The frequent recurrence of disease reactivation was expected in the control arm (Wada 2014). An 8-week event rate was assumed to be 90% in the placebo group and a considerable reduction in disease reactivations for subjects receiving Tadekinig alfa was expected. However, a lower event was observed from the currently enrolled (still blinded) patients. Thus, the RW phase is prolonged to a maximum of 16 weeks to better assess the effect of Tadekinig alfa withdrawal. The power calculations below will assume the same 90% event rate in the SOC arm at 16 weeks.

The figure below displays the power achieved for a two-arm study with a 1:1 randomization of 10 subjects, based on two-sided alpha=0.05, a 16-week event rate of 90% in the control arm, and assumed hazard ratios that vary from 0.1, 0.15, 0.2, and 0.25.

Figure 1: Power vs. Hazard Ratio

A hazard ratio of 0.1 equates to an assumed 16-week event rate in the Tadekinig alfa group of 20.6% (i.e., a survival event-free rate of 79.4%). These assumptions achieve 78.4% power based on a two-sided log rank test with an overall sample size of 10 patients to be randomized in the RW phase (5 in the placebo group and 5 in the Tadekinig alfa group). A hazard ratio of 0.1 results in an assumed number of total events among 10 patients to be 6.7, with 4.9 occurring in the placebo group and 1.8 occurring in the Tadekinig alfa group.

No power calculations were performed for the SAOL phase of the study, as analysis will be descriptive in nature.

7 SCHEDULE OF EVENTS

Table 1: Schedule of Events -- Note: Flexibility in the visit scheduling is allowed (± 3 days) for V2 through V13 – The table shows week numbers approximately

	SAOL Phase ^h									RW Phase					
	Prior to V1 V0 Screening Visit	W 0 V1/ Day0 Baseline	W1 V2/ Day7 SOC Taper	W2 V3/ Day14 SOC Taper	W3 V4/ Day21 SOC Taper	W4 V5/ Day28 SOC Taper	W 8 V6/ Day 56	W 12 V7/ Day 84	W18 V8/ Day 126	W20 V9/ Day 140	W22 V10/ Day 154	W26 V11/ Day 182	W30 V12/ Day 210	W34 V13/ Day 238 Study completion	
Review and signing of Child Assent and Informed Consent Form (ICF)	X														
Demographics and medical history (previous treatments and comorbidities)	X														
Ophthalmic examination		X													
Inclusion/exclusion criteria review	X	X ^a													
Physical exam with specific assessment of hepatosplenomegaly and vital signs	X ^k	X	X	X	X	X	X	X	X	X	X	X	X	X	X
Randomization to Tadeking alfa or placebo (applicable for the RW phase only)		N/A								X					
Standard of Care (SOC) Tapering ^f		X	X	X	X	X									
Treatment with Tadeking alfa (SAOL phase only)		X	X	X	X	X	X	X	X						
Treatment with Tadeking alfa or placebo as randomized in the double blind RW phase (s.c. every 2days) ^b										X ^l	X	X	X	X	X
Review of adverse events (AEs, AESIs) & concomitant medications	X	X	X	X	X	X	X	X	X	X	X	X	X	X	X
Local Tolerability Index assessment ^c		X	X	X	X	X	X	X	X	X	X	X	X	X	X
Physician global clinical evaluation: mAIDAI	X	X	X	X	X	X	X	X	X	X	X	X	X	X	X
Physician Global Assessment (PGA)	X	X	X	X	X	X	X	X	X	X	X	X	X	X	X
Patient's/caregiver's evaluation of health status		X								X					X
Genetic evaluation, infection evaluations (CMV, EBV, etc.), and serology (HIV, HCV, HBV),	X														
Hematology, clinical chemistry, ESR (at local lab), urinalysis, CRP and Ferritin, coagulation (platelets, fibrinogen, D-dimer, PTT, PT) -- (sample taken prior to treatment), pregnancy test ^g ^l TB blood test ^d ^l	X ^l	X	X	X	X	X	X	X	X ^l	X	X	X	X	X	X

Flow Cytometry ^m	X													
Serum: Total IL-18, free IL-18, IL-18BP (sample taken prior to treatment)	X	X	X	X	X	X	X	X	X	X	X	X	X	X
Anti-Tadekinig alfa antibodies (sample taken prior to treatment)		X		X		X		X	X		X	X		X
PK study measurements ^e		X ^e				X ^e								

CMV = cytomegalovirus; CRP = C-reactive protein; EBV = Epstein-Barr Virus; ESR = erythrocyte sedimentation rate; FU = Follow up; HBV = hepatitis B virus; HCV = hepatitis C virus; HIV = Human Immunodeficiency Virus; ICF = Informed Consent Form; IL-18 = interleukin-18; IL-18 BP = interleukin-18 binding protein; mAIDAI = Modified Autoinflammatory Disease Activity Index; PK = pharmacokinetic; PT = prothrombin time; PTT = partial thromboplastin time; RW = Randomized Withdrawal phase; SAOL phase = Single arm open label phase; s.c. = subcutaneous; TB = tuberculosis

- a Reassessment of inclusion/exclusion criteria prior to treatment start
- b Investigational product (Tadekinig alfa or placebo) will be administered every 2 days \pm 5 hours to the patient. If the patient is located within close vicinity to the site, s/he has the option to go to the site for treatment administration or a Home Care Nurse may administer the treatment at the patient's residence. At V1 (Week 0), the first dose will be administered at the study center and the patient will remain at the site for a 2-hour observation.
- c Local Tolerability Index will be assessed by the Investigator or study nurse at the in-clinic visits including Week 0/Visit 1 when patient is at site under observation after first dose, and by the home care nurse on the subject's dose administration days, approximately every other day.
- d TB blood testing (QuantiFERON TB test) should be done at the local (hospital) lab or central lab, prior to treatment initiation
- e Additional sample for PK study will be collected at V1 and V5 prior to treatment and at 2 h, 4 h, 6 h and 24h post treatment (with a +/- 30 minutes window at each sample collection). Trough levels are calculated based on blood samples used for lab testing (no extra sample needed). Patients who are not hospitalized will need to present to the site 24h post-treatment for final PK sample collection, as well as AE and concomitant medication assessments.
- f If the patient has a disease reactivation during the tapering down, 28-day (4-week) SOC tapering cycles may be used and can be repeated during the 18-week SAOL study period.
- g A urine pregnancy test will be performed at each study visit on all females of childbearing potential. If the urine pregnancy test is positive, a serum pregnancy test will be performed.
- h W18/Visit 8 will serve as the End of the SAOL period visit for those patients who discontinued treatment during the SAOL phase (an early termination form should be completed for these patients). These patients will not continue into the RW phase of the study.
- i Treatment of study drug administered to patients at W18/Visit 8 would be determined by randomization into RW phase. Final dose of treatment under the SAOL phase of the study will occur 2 days prior to W18/Visit 8. All W18 assessments must be performed prior to administration of study drug at W18/Visit 8.
- K Height collected at screening
- l Collection of Baseline lab samples may occur up to 3 days prior to the scheduled Week 0/Day 0 and Week 18/ Day 126 visit in order to have results available to confirm patient eligibility prior to study treatment.
- m Flow cytometry studies are necessary when a XIAP genetic abnormality has been found in the genetic testing. It is not required for patients with NLRC4 genetic mutations.

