In the absence of an approved medication for this disease, the SOC as defined in this protocol consists of glucocorticoids (GC), with a 28-day tapering schedule as follows:

- 28-days (4 weeks): Daily PO/IV Dexamethasone 10 mg/m² x 7 days, 5mg/m² x 7 days, 2.5 mg/m² x 7 days, 1.25 mg/m² x 7 days

Patients who respond to the initial TA + GC 28-day course (see Definition of Partial and Complete Response to Therapy) will receive Tadekinig alfa for 14 additional weeks.

Patients who responded to TA + SOC initial course and have a disease reactivation again during the course of the study will receive another course of TA + SOC with the same GC dosage and tapering schedule used for the initial treatment of the active disease (see explanations below). Maintenance treatment, with the permitted medications, at stable and at the same doses utilized at study entry are allowed. Dose increments for the permitted co-medications or their introduction after the beginning of the study are not permitted and represent treatment failures and study early termination. If permitted co-medications are weaned off during the course of the study and the investigator decides to re-introduce them, they are permitted as long as the doses are the same or lower than the doses used at study entry.

Upon lack of response to combined treatment after enrollment or upon the occurrence of a disease reactivation during the course of the SAOL after initial response, the investigator may decide to treat the patient with rescue immunosuppressors. This decision results in patient discontinuation for the study.

Tadekinig alfa will be administered at 2 mg/kg subcutaneously (s.c.) for up to approximately 18 weeks.

At V0 and V1, patients will undergo a physical examination, measurement of vital signs, and routine laboratory testing (including hematology, clinical chemistry, urinalysis, erythrocyte sedimentation rate (ESR), CRP, and coagulation panel). Biological evaluation and genetic diagnosis of autoinflammatory conditions (NLRC4-MAS, XIAP deficiency, and other monogenic associations with Macrophage Activation Syndrome [MAS]) will be done at V0. Samples for flow cytometry will be analyzed during the screening period and prior to V1. Complete medical and disease history will also be collected during V0. In addition, prior to initiation of therapy, cytomegalovirus (CMV) and Epstein-Barr virus (EBV) tests, serology tests, and a complete infectious workup will be performed.

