At RW visits, patients will undergo a complete physical examination and laboratory testing (including hematology, clinical chemistry, urinalysis, ESR, CRP, ferritin, and coagulation panel), determinations of total and free IL-18 and of IL-18 BP. The mAIDAI and PGA will be applied at all visits in the RW phase. The patient's or caregiver's evaluation of the health status questionnaire will be applied at the end of the RW phase.

Samples for anti-drug antibodies (ADAs) will be collected at RW Week 22 (V10), Week 26 (V11), and Week 34 (V13).

During the RW phase, patients who develop a partial or full disease reactivation before the 16-week treatment is completed will proceed to the End of Study visit and complete the RW phase. The investigator may also decide to start rescue immunosuppression and discontinue treatment.

If applicable, data on administration of other medications or rescue immunosuppression during both phases (SAOL and RW) will be collected, including the time of treatment start and finish and whether or not there was a response to the rescue treatment.

Patients who discontinue treatment prior to the end of either treatment phase (SAOL or RW) will be followed for all key efficacy and safety assessments.

NOTE: The FDA draft guidance (Enrichment Strategies for Clinical Trials to Support Approval of Human Drugs and Biological Products, December 2012) indicates that the RW design should include patients who demonstrated treatment response.

- Additional Standard of Care Cycles or Rescue Immunosuppression in SAOL Phase:

A) If no response after the first combined treatment course (SOC + IMP) at the initiation of the SAOL phase:

If patients do not respond to therapy (see Definition of Partial and Complete Response to Therapy and Disease Improvement) after the initial combined treatment course, they will be treated with rescue immunosuppression or with new/ increased doses of Permitted Concomitant Treatments. Patients treated with rescue immunosuppression or new/ increased doses of Permitted Concomitant Treatments will be considered treatment failures and exit the study

B) Patients with a disease reactivation after having responded to therapy in the SAOL Phase.

If patients show signs of systemic inflammatory reactivation (i.e. partial or full disease reactivation) after having responded to therapy in the SAOL phase, they will receive another cycle of SOC in addition to the IMP.

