Complete and partial response to therapy from week 10 onwards was added as new key secondary endpoint. The evidence provided in the open label part to control the disease after the patients have entered the study in a status of high inflammatory activity is a crucial part to provide evidence of the efficacy of Tadekinig alfa treatment. The 10-week time point to begin assessing the response to therapy was chosen based on the timeline for steroid discontinuation and the need for the residual effect of steroids to no longer be present. Per the protocol, patients may receive Tadekinig alfa in addition to standard of care systemic steroids. The steroids are tapered down by day 28 after study initiation. However, a patient may receive another 28 day cycle of steroids upon initial disease reactivation, which is expected to occur during or shortly after the first steroid tapering. This results in a total expected time of 8 weeks of steroid taper. If patients are not stabilized after the second steroid taper, they are expected to start rescue immunosuppression and discontinue study treatment. Therefore, at week 10, patients are expected to no longer require steroids and any residual effects will not be present.

A patient's or caregiver's qualitative evaluation of health status was added with protocol version 6. Given the heterogeneous patient population (age range, disease symptom and impacts) and regulatory concerns that generic validated quality of life questionnaires would not be fit-for-purpose for use in this trial to support regulatory decisions, a non-validated questionnaire specifically designed for this patient population and study design is used. It captures the patient's or caregiver's qualitative evaluation of health status similar to the physician global assessment (PGA), the severity of individual symptoms and the perceived change in symptoms at the end of the SAOL and RW phase.

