7.4.3 Key Secondary Efficacy Endpoint Analysis Methods

The key secondary efficacy endpoint is response to therapy (including complete response and partial response) in the SAOL phase from Week 10 onwards and observed at least 2 consecutive visits at least 2 weeks apart. Patients who do not achieve complete response or partial response at 2 consecutive visits at least 2 weeks apart at Week 10 onwards or drop out prior to Week 10 will be considered non-responders. Patients who respond to therapy in the SAOL phase with complete or partial response will be summarized by the number and percent of patients along with the associated 95% exact Clopper-Pearson CIs.

The estimand for this endpoint will be described as:

Population: All patients in the SAOL-FAS population

Endpoint: Responder or non-responder.

Intercurrent events:

- Discontinuation prior to Week 10: patients who discontinue prior to Week 10 will be assigned as non-responders.
- Rescue immunosuppression treatment: patients who receive rescue immunosuppression treatment and continue in the SAOL phase and satisfy the criteria of responder will be considered responders.

Population-level summary: Number and percentage of responders and 95% exact Clopper-Pearson CIs.

A sensitivity analysis will also be performed that only considers assessments up to the start day of the rescue immunosuppression treatment.

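### The Week 10 start of the key secondary endpoint assumes steroids are finished, but repeat SOC cycles have no last start day and the SAP estimand does not address them

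*Protocol*

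**What the plan says.** **Reason for Week 10.** Protocol 8.3.3 says of the first course: "The steroids are tapered down by day 28 after study initiation". It allows for a second 28-day cycle at an initial reactivation, during or shortly after the first taper, and adds: "This results in a total expected time of 8 weeks of steroid taper". It continues: "If patients are not stabilized after the second steroid taper, they are expected to start rescue immunosuppression and discontinue study treatment". Its conclusion is: "Therefore, at week 10, patients are expected to no longer require steroids and any residual effects will not be present".

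**Repeat cycles.** The SOC course in the Protocol Synopsis is "28-days (4 weeks): Daily PO/IV Dexamethasone" at tapering doses. Case B (Synopsis and Section 9.1, repeated in SAP 6.1.4) covers patients who reactivate "after having responded to therapy in the SAOL phase, they will receive another cycle of SOC in addition to the IMP". Case C gives another full 4-week cycle for reactivation during the taper. Table 1 footnote f, also conditioned on reactivation during tapering, says "28-day (4-week) SOC tapering cycles may be used and can be repeated during the 18-week SAOL study period". None of these gives a last start day.

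**Endpoint and response definition.** The endpoint is complete or partial response from Week 10 at two consecutive visits at least 2 weeks apart. Partial response (Protocol 12.1, SAP 6.4.1.2) needs at least a 50% reduction in affected organ categories plus one of two things: normalisation of at least half of the markers raised at baseline, or discontinuation of steroids or other immunosuppressants that were ongoing at baseline.

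**Analysis.** SAP 7.4.3 states: "Patients who respond to therapy in the SAOL phase with complete or partial response will be summarized by the number and percent of patients", with exact confidence intervals. It names two intercurrent events, discontinuation before Week 10 and rescue immunosuppression. Its one sensitivity analysis cuts at the start of rescue.

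**The concern.** Week 10 was chosen so that response would be read without steroid effect, and 8.3.3 treats open-label disease control as essential evidence of efficacy. The operative sections leave three openings.

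- The marker route to partial response has no steroid condition. The discontinuation criterion, which is also part of complete response, is tied to therapy ongoing at baseline, so it is unclear whether a later repeat cycle disqualifies a visit.
- Open-label reactivation is judged against the previous visit, but response is judged against baseline. A patient can therefore be re-treated for reactivation and still meet partial response.
- Glucocorticoids are not among the rescue drugs listed in Protocol 11.2.4, which names SOC among the allowed treatments. A repeat SOC cycle is thus neither an intercurrent event in SAP 7.4.3 nor touched by its sensitivity analysis.

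A plan followed to the letter can therefore count a visit supported by dexamethasone as a response to the study drug.

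**Working it through.** **Inputs.** Cycle length 28 days (Synopsis). Scheduled visits from Week 10 to the end of the open-label phase: V7 on Day 84 and V8 on Day 126, each ±3 days (Table 1). Maximum enrolment 15 (Synopsis).

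**The plan's figure.** 2 × 28 = 56 days = 8 weeks, as 8.3.3 states. Week 10 is Day 70, and 70 − 56 = 14 days of margin. A cycle started on day s is dosed from s to s + 27.

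- To be off steroid by Day 70: s + 28 ≤ 70, so s ≤ 42.
- To keep the 14-day margin as well: s + 28 + 14 ≤ 70, so s ≤ 28, which is back to back with the first course.

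**Start days that reach a visit on day V.** Assessment precedes a cycle started on the same day. Dosing at the visit requires V − 27 ≤ s ≤ V − 1. Dosing on that day or in the 14 days before requires V − 41 ≤ s ≤ V − 1.

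| Visit | Dosing at the visit | On that day or in the 14 days before |
|---|---|---|
| Week 12 (Day 84) | Day 57 to 83 | Day 43 to 83 |
| Week 18 (Day 126) | Day 99 to 125 | Day 85 to 125 |

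**Can one cycle cover both visits?** V7 and V8 are 126 − 84 = 42 days apart (36 to 48 with the windows), so one 28-day cycle cannot be dosed at both. Counting the 14-day allowance, one cycle reaches both only if the visits are no more than 40 days apart. That does not happen on nominal days, but can when windows bring them closer (for example Day 87 and Day 126, start Day 85 or 86). Two later cycles, such as starts on Day 57 and Day 99, are dosed at both.

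**Why one visit is enough.** On scheduled visits a responder needs both V7 and V8. If one is met without steroid and the other only with it, the steroid-supported visit completes the pair. SAP 7.1.3 also lets unscheduled visits enter multi-visit derivations, so a cycle started on Day 71 to 83 is dosed both at Day 84 and at an unscheduled Day 98 visit, exactly 2 weeks apart.

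**Size.** 1/15 = 6.7 percentage points per patient, and more if the denominator is smaller. As an illustration, assume 15 patients and 10 responders (the documents give no expected rate), with Clopper-Pearson 95% intervals:

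- none reclassified: 10/15 = 66.7% (38.4 to 88.2)
- one reclassified: 9/15 = 60.0% (32.3 to 83.7)
- two reclassified: 8/15 = 53.3% (26.6 to 78.7)
- three reclassified: 7/15 = 46.7% (21.3 to 73.4)

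**The case against.** **The conflict is softer than it first appears.** A reader might infer that 8.3.3 caps steroids at 8 weeks and that footnote f permits cycles at any time. Neither is supported. The 8 weeks is an expectation, 8.3.3 also expects rescue and discontinuation after a failed second taper, and footnote f is limited to reactivation during tapering. This stands. The point rests mainly on case B, and the rescue expectation is not written as a rule in the treatment sections.

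**Exposure at the visits is limited.** On nominal days a cycle started at V6 (Day 56) ends on Day 83, and one started at V7 ends on Day 111, 15 days before V8. Dosing at V7 or V8 therefore needs a start between nominal visits, although V6 held one day late is enough (57 + 27 = 84). A reader might also infer that one cycle can produce both required responses at V7 and V8. On nominal days it cannot. What remains is that one supported visit can complete the pair.

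**The stakes are modest and the data are visible.** The endpoint is descriptive and outside the testing hierarchy (SAP 7.7). Reactivations, concomitant medications, weekly glucocorticoids and individual plots are all planned, so re-treated patients can be identified. This stands, but the responder percentage itself is not adjusted.

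**A steroid-free rule could distort the endpoint.** On nominal days a 14-day rule voids V7 or V8 for every start after Day 42 and before V8 except Day 84 itself, however well controlled the patient is later. The 14 days is inferred from the Week 8 to Week 10 gap; the protocol states no washout. This stands and argues against making the rule the main definition.

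**Randomized phase.** A reader might infer that steroid carried past V8 biases the primary comparison. The documents do not support a directional bias, because assignment at V8 is blinded and 1:1. The extreme case, a start on Day 125, runs to Day 152, or 27 of the randomized-phase days, and needs a patient who reactivates just before V8 yet still meets response there.

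**Conclusion.** The concern holds in this limited form. The rationale for Week 10 is not secured by the treatment rules, the response definition or the SAP estimand. The key secondary responder rate can include visits supported by repeat SOC steroid, and neither the main analysis nor its sensitivity analysis would show it.

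The exposure is mainly through partial response and normally through one of the two scheduled visits. Each affected patient is worth about 6.7 points or more. How many patients receive a late cycle cannot be known from the documents, so this is the size per patient, not a forecast. The Day 43 to 83 and Day 85 to 125 ranges assume a 14-day carry-over; the Day 57 to 83 and Day 99 to 125 ranges do not.

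For the primary endpoint, the expected effect of steroid still being given at V8 is fewer early events and lower power.

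**What to change.** 1. Reconcile Protocol 8.3.3 with Table 1 footnote f and with cases B and C in the Synopsis and Section 9.1 (and SAP 6.1.4), so that the stated reason for Week 10 and the repeat-cycle provisions agree. No treatment rule is proposed here.
2. Keep the current responder definition. Add to SAP 7.4.3, before unblinding, a supportive responder analysis in which a visit with protocol SOC glucocorticoid on that day or in the previous 14 days does not count as a response visit. Report it beside the main result, with the number of patients whose classification changes.
3. Optionally, add a sensitivity analysis of the primary endpoint that flags patients on SOC glucocorticoid at V8.

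The cost is SAP wording and one or two extra outputs from concomitant-medication and glucocorticoid data already collected. The supportive rate can only equal or fall below the main rate. It will count most patients re-treated after Day 42 as non-responders, including some who were well controlled afterwards, so it should be read as a lower companion figure and not as a replacement.
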